COVID related events (events with MedDRA COVID-19 SMQ narrow selection) will be listed. This listing will include all collected AE information and additionally the cycle, onset since first efgartigimod dose, onset since last efgartigimod dose before AE onset, last total IgG before AE onset, the last percent change in total IgG before AE onset and the time when that reported total IgG was taken compared to AE onset.

5.2 CLINICAL LABORATORY EVALUATION

5.2.1 Available data

Per protocol, the following laboratory parameters are expected:

- Biochemistry: blood urea nitrogen (BUN), creatinine, creatinine clearance (unadjusted), glucose (fasting for 8 hours), total calcium, glycosylated hemoglobin (HbA1c), potassium, sodium, alkaline phosphatase (ALP), lactate dehydrogenase (LDH), C-reactive protein (CRP), aspartate aminotransferase (AST), alanine aminotransferase (ALT), gamma-glutamyl transferase (GGT), total bilirubin, direct bilirubin, albumin, lipid panel (total cholesterol, high density lipoprotein (HDL), low density lipoprotein (LDL), and triglycerides), international normalized ratio (INR), prothrombin time (PT), and activated partial thromboplastin time (aPTT).
- Hematology: platelet count, red blood cell count (RBC), hemoglobin, hematocrit, RBC indices (mean corpuscular volume (MCV), % reticulocytes), white blood cell (WBC) count with WBC differential (% and absolute for neutrophils, lymphocytes, monocytes, eosinophils, basophils).
- Urinalysis:
 - Continuous: specific gravity, pH
 - Categorical: glucose, protein, blood, ketones, bilirubin, nitrite, leukocyte esterase, microscopic evaluation, highly sensitive urine human chorionic gonadotropin (hCG) pregnancy test for females of childbearing potential.
- Other: Serum and urine human chorionic gonadotrophin (β -HCG), Follicle-stimulating hormone (FSH) test, SARS-CoV-2 testing
- Specialty laboratory tests: may include but not be limited to apolipoprotein B (apoB), lipoprotein A, fibrinogen, von Willebrand factor, d-dimer.

Normal ranges are available as provided by the laboratory.

5.2.2 *Derivation rules*

The following parameters will be derived:

- Estimated glomerular filtration rate (eGFR) (Chronic Kidney Disease Epidemiology Collaboration (CKD-EPI)) (mL/min/1.73m²)
= 141 * minimum(creatinine (mg/dL)/ K; 1)^α *
maximum(creatinine (mg/dL)/K; 1)^{-1.209} * 0.993^{age (years)} *
[1.018 if female] * [1.159 if race = black]

where K = 0.7 if female and K = 0.9 if male; $α$ = -0.329 if female and $α$ = -0.411 if male

Note: in case results in mg/dL are not available, results in μ mol/L will be used after conversion in mg/dL: 1 mg/dL = 88.4 μ mol/L

- Only fasted lipid samples and glucose (missing fasting status is considered as non-fasted) will be included in tabulations
- The following lipid ratios will be calculated based on fasted samples only (missing fasting status is considered as non-fasted) and rounded as detailed in section 2.3.3:
 - total cholesterol/HDL
 - LDL/HDL
 - HDL/LDL
- The following abnormality categories will be defined:
 - Low: value < lower limit of normal range
 - Normal: lower limit of normal range \leq value \leq upper limit of normal range
 - High: value > upper limit of normal range

Note:

- Classification will be done in standardised units, using non imputed values and limits.
- For the worst-case analysis visits, as defined in section 2.2.5, an additional category low + high is defined in case there are both low and high post-baseline values.

Toxicity grades will be based on the common toxicity criteria for adverse events (CTCAE) toxicity grading list (version 5.0). The implementation of these toxicity grades for analysis is presented in appendix 9.2. Only the parameters described in appendix 9.2 will be computed, according to the declared limits for each grade.

5.2.3 *Presentation of results*

The statistical analysis will present results in standardised units, except for corrected GFR, which will be reported in mL/min/1.73m².

Continuous laboratory parameters will be summarized by means of descriptive statistics at each analysis visit by cycle and over time. Actual values and changes from baseline will be shown in the same table. Categorical urinalysis results will be listed only.

Statistical Analysis Plan

ARGX-113-2002

Final Analysis

Final 5.0 of 31Jan2025

Laboratory abnormalities will be presented as cross-tabulations of the abnormality at each post-baseline analysis visit and at the worst-case analysis visit versus the baseline abnormality. Numbers of participants with treatment-emergent abnormalities (see Definition of terms) will also be shown. The denominator for the percentage is the total number of participants having data for the parameter per treatment and per analysis visit in the safety analysis set.

Laboratory toxicity grades will be presented as cross-tabulations of the toxicity at each post-baseline analysis visit and at the worst-case analysis visit versus the baseline toxicity. Numbers and cumulative numbers over decreasing toxicity grading of participants with treatment-emergent toxicities will also be shown. The denominator for the percentage is the total number of participants having data for the parameter per treatment and per analysis visit in the safety analysis set. Parameters having toxicity grades defined in both directions (hypo and hyper) will be shown by direction.

Both cross-tabulations will be repeated by average treatment duration per year. All laboratory data will be listed, but only for participants with any post-baseline abnormality.

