A=day 1 of a TP; ADA=antidrug antibodies; AE=adverse event; eCRF=electronic case report form; ECG=electrocardiogram; EoS=end of study; ET=end of treatment; FSH=follicle-stimulating hormone; gMG=generalized myasthenia gravis; ICF=informed consent form; IMP=investigational medicinal product; IP=intertreatment period; IP_nVm=IP (period number) visit (visit number); MG-ADL=Myasthenia Gravis Activities of Daily Living; NA=not applicable; NAb=neutralizing antibody; PBMC=peripheral blood mononuclear cell; PH20=recombinant human hyaluronidase PH20 (rHuPH20); PHQ-9=9-item Patient Health Questionnaire; SC=subcutaneous(ly); SFU=safety follow-up; SIB=Suicidal Ideation and Behavior; SoA=schedule of activities; TP=treatment period; TP_nVm=TP (period number) visit (visit number); UNS=unscheduled; (X)=optional activity, only done under specified conditions; Y=previous IP period visit
Note: All activities will be performed predose on dosing days, unless otherwise indicated. If a participant enters year 2 of the study during a TP, the remaining TP visits and subsequent IPnV1 must be completed according to the year 1 SoA (refer to [Table 1](#)).

^a IPnV1 can become a TPn+1V1 if there are at least 7 days past the last IMP administration in the previous TP, and the participant is in need of retreatment. All IPnVm visits may also become a new TP, if the investigator determines there is a need for retreatment. The need for retreatment will be assessed prior to performing any activities, so that only activities listed for IPnV1/m or TPn+1V1 are performed, respectively. The visit denominator ("m") will start at 2 for each IP after a TP.

^b Participants will remain in the study for at least 1 year, until efgartigimod PH20 SC becomes commercially available or available through another continued access program for gMG, or until 31 Dec 2024, whichever comes first.

^c On-site visits are required for TPnV1, for IPnV5/10/15, etc, (ie, every 5 visits), and for ET, EoS, and SFU visits. All other visits in Table 2 can be performed by phone, including TPnV2/3/4 in case of IMP home administration.

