^d For participants who discontinue early from the study, the activities will depend on the visit at which the participant had to discontinue. Participants who discontinue early from the study at either a TP visit or an IP visit should perform planned activities for the ET visit if 49 (±2 days) days has not elapsed since the last dose of efgartigimod. These participants will not receive any further administration of efgartigimod PH20 SC during the study and will return for the SFU visit 49 ±2 days after the last dose administration. If 49 ±2 days has already elapsed since the last administration of efgartigimod PH20 SC, then this visit becomes the SFU visit and the SFU visit activities must be performed. Participants who discontinue early from the study between visits should perform the SFU visit at least 49 ±2 days after the last dose administration. If 49 ±2 days has already elapsed since the last administration of efgartigimod, then the SFU visit will be planned as soon as possible.

^e A UNS visit can occur at the request of the participant or the investigator. During the UNS visit, activities indicated in the SoA can be performed at the discretion of the investigator, depending on the reason for the UNS visit.

^f It is recommended to perform the MG-ADL scale prior to all other activities.

^g The SIB Risk Monitoring assessment is based on question 9 of the PHQ-9.

^h These assessments will only be performed every 5 visits (IPnV5, IPnV10, etc).

ⁱ Blood samples for clinical laboratory (hematology/clinical chemistry/coagulation panel and FSH, if applicable) safety assessments will be collected. See Section 10.2. Participants will need to be fasted for each on-site visit at which safety laboratory assessments are collected. Fasted is defined as no food or drink at least 8 hours prior to each sampling. Permitted medications that the participant normally takes can be taken as usual before a visit.

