6.5.1. Retreatment Criteria

A participant may be retreated if the investigator determines that the participant's condition has deteriorated due to gMG symptoms and if the participant agrees to be retreated.

The investigator may start a new TP during an on-site IP visit. In this instance, the IP visit becomes the first visit of the new TP (TP_nV1). No activities will be duplicated. If a participant thinks they may need retreatment between on-site visits, they may contact the investigator to discuss retreatment and schedule the first visit of the new TP (TP_nV1).

The participant must meet all of the following criteria to be eligible for retreatment:

- The participant completed the previous TP
- The participant could benefit from retreatment according to the investigator's judgment
- There is no clinical or laboratory evidence of any concomitant disease that could confound the results of the study or put the participant at undue risk (eg, infection)
- At least 28 days has elapsed since the participant received any kind of rescue therapy
- For year 1:
 - At least 28 days has elapsed between treatment periods (ie, between the last dose of the previous TP and the first dose of the next TP)
- For year 2 onward:

- At least 7 days has elapsed between treatment periods (ie, between the last dose of the previous TP and the first dose of the next TP). It is recommended to have intertreatment periods (IPs) of at least 28 days, but a subsequent treatment period can be administered earlier based on clinical evaluation at the discretion of the investigator.
- There must be at least 4 weeks left in the study for the participant, so that a full TP and the EoS visit can be performed.

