9.2. Sample Size Determination

No sample size calculation is needed in this study. Up to 201 participants may be enrolled from the antecedent studies ARGX-113-2001 and ARGX-113-1705.

Note: “Enrolled” means a participant’s agreement to enter a clinical study following completion of the informed consent process and screening. Potential participants who are screened for the purpose of determining eligibility for the study, but do not participate in the study, are not considered enrolled, unless otherwise specified by the protocol.

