2.2.5 Worst-case

A worst-case analysis visit will be created for parameters for which abnormalities and/or toxicity grades are defined to summarize values considered as the worst-case. Abnormalities are derived per parameter, and if both the lowest and the highest values

	Statistical Analysis Plan	
ARGX-113-2002	Final Analysis	Final 5.0 of 31Jan2025

are considered abnormal, then two worst-case analysis visits for the same parameter will be presented for the participant. For toxicity grades, the worst-case value of toxicity grades is associated with the highest toxicity grade and is derived per parameter and by toxicity direction (hypo/hyper).

All non-missing post-baseline values within the treatment and follow-up phase, including unscheduled assessments will be considered when deriving the worst-case analysis visit.

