5.3.3 Presentation of results

Vital signs parameters supine SBP, DBP and pulse rate will be summarized by means of descriptive statistics at each analysis visit by cycle and over time. Actual values and changes from baseline will be shown in the same table.

Abnormalities will be presented as cross-tabulations of the abnormality at each post-baseline analysis visit versus the baseline abnormality and as cross-tabulations of the worst-case abnormality versus the baseline abnormality. Numbers of participants with

Statistical Analysis Plan

ARGX-113-2002

Final Analysis

Final 5.0 of 31Jan2025

treatment-emergent abnormalities will also be shown. The cross-tabulation will be repeated by average treatment duration per year.

All vital signs data will be listed, but only for participants with any post-baseline abnormality.

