5.4.3 Presentation of results

Uncorrected QT interval and RR will only be listed.

Continuous ECG parameters will be summarized by means of descriptive statistics at each analysis visit by cycle and over time. Actual values and changes from baseline will be shown in the same table.

Abnormalities of the actual values will be presented as cross-tabulations of the abnormality at each post-baseline analysis visit, and at the worst-case analysis visit

	Statistical Analysis Plan	
ARGX-113-2002	Final Analysis	Final 5.0 of 31Jan2025

versus the baseline abnormality. Numbers and cumulative numbers over decreasing abnormalities (QTc only) of participants with treatment-emergent abnormalities will also be shown. The denominator for the percentage is the total number of participants having data for the parameter per treatment and per analysis visit in the safety analysis set.

Abnormalities of the QTc changes will be presented as tabulations of the change abnormality at each post-baseline analysis visit and at the worst-case analysis visit. Cumulative numbers over decreasing change abnormalities of participants will also be shown. The denominator for the percentage is the total number of participants having data for the parameter per treatment and per analysis visit in the safety analysis set.

The cross-tabulation and the tabulation of QTc change will be repeated by average treatment duration per year.

All ECG data will be listed, but only for participants with any post-baseline abnormality.

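### From year 2, labs, vital signs and ECGs are scheduled about once per cycle, so at similar follow-up the worst-case rows by treatment-duration group are expected to show more abnormalities in the most-treated group even with no drug effect

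*SAP*

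**What the plan says.** **Schedule.** Protocol 1.3, Table 2 (year 2 onward) places safety labs, vital signs and ECG at the first visit of each treatment period (TPnV1), at selected intertreatment visits and at ET/EoS/SFU. Unscheduled visits are at the investigator's discretion. Footnote h limits the intertreatment visits: "These assessments will only be performed every 5 visits (IPnV5, IPnV10, etc". Footnote c sets the on-site visits to match: "On-site visits are required for TPnV1, for IPnV5/10/15, etc, (ie, every 5 visits), and for ET, EoS, and SFU visits". None of these assessments is scheduled at TPnV2-V4 or IPnV1. Protocol 6.5.1 sets the year 2 minimum gap: "At least 7 days has elapsed between treatment periods".

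**Grouping.** SAP 2.4.3 classes mSAF participants by 365 x completed cycles / total duration x 4, with cuts at 30 and 38 weeks per year. The data start with the cycle in which the v3.0 consent was signed.

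**Worst case.** SAP 2.2.5: "All non-missing post-baseline values within the treatment and follow-up phase, including unscheduled assessments will be considered when deriving the worst-case analysis visit". The denominator in SAP 5.2.3 and 5.4.3 is participants with data for the parameter.

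**Repeats by group.** Labs: "Both cross-tabulations will be repeated by average treatment duration per year". Vital signs (SAP 5.3.3): "The cross-tabulation will be repeated by average treatment duration per year". ECG (SAP 5.4.3): "The cross-tabulation and the tabulation of QTc change will be repeated by average treatment duration per year". The outputs are Tables 14.3.2.2B, 14.3.2.3B, 14.3.3.2B, 14.3.4.2B and 14.3.4.3B.

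For adverse events, SAP 5.1.2 defines rates per 100 patient-years of follow-up. These five tables have no counterpart and no adjustment for number of samples.

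**The concern.** A participant with cycles up to about 112 days has one scheduled set of assessments per cycle, and the exposure group is itself a function of cycles per year. The group label therefore largely fixes how often abnormalities are looked for. A worst-of-all-values summary with one count per participant grows with the number of looks, so a gradient across groups can appear when the drug does nothing.

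SAP 2.4.3 creates these groups to examine safety under increased exposure, and labs, vital signs and ECG are part of the primary endpoint. A reader who compares worst-case rows across the three columns could take a sampling artefact for a dose-frequency signal. The rest of the plan gives little to check against: continuous summaries of these parameters have no version by duration group, and the listings cover only participants with an abnormal value, so per-sample denominators cannot be recovered.

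**Working it through.** **1. Reproduce the plan's own figure.** SAP 2.4.3 states up to 52 injections per year from year 2, against 30 in year 1. With cycle length L days, injections per year = 365 / L x 4.
- Year 2 minimum: L = 21 + 7 = 28, giving 52.1.
- Year 1 minimum: L = 21 + 28 = 49, giving 29.8.

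Both agree.

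**2. Convert the cuts to cycle lengths.** 365 x 4 / 30 = 48.7 days; 365 x 4 / 38 = 38.4 days.

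**3. Scheduled sets per year on the year 2 schedule.** IPnV1 is at A+28 and later visits come every 21 days, so IPnV5 falls at A + 28 + 4 x 21 = A+112, IPnV10 at A+217 and IPnV15 at A+322. Sets per cycle = 1 (TPnV1) plus one for each of these reached. ET/EoS/SFU and unscheduled samples are left out.

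| Group (weeks/year) | Cycle length, whole days | Sets per year |
|---|---|---|
| >38 | 28-38 | 9.6-13.0 |
| >30 to <=38 | 39-48 | 7.6-9.4 |
| <=30 | 49 or more | 3.3-7.4 |

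The lowest figure is at L = 112 (365 / 112 = 3.3). It drops to 2.6 if every visit uses the full +7-day window (365 / 140). The ranges do not overlap.

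**4. Chance of at least one abnormal value with no drug effect, one year.** The per-sample probability p and within-person correlation r are assumptions; the documents give neither. For m samples:
- Independent: 1 - (1 - p)^m. At p = 5%: 1 - 0.95^13 = 48.7%; 1 - 0.95^7 = 30.2%.
- Correlated (beta-binomial): with s = (1 - r)/r, a = ps and b = (1 - p)s, the chance is 1 minus the product over i = 0 to m-1 of (b + i)/(a + b + i).

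Samples are rounded down to whole sets: 13, 8, 7 and 5 for 28-, 42-, 50- and 70-day cycles.

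| p | r | 28 d | 42 d | 50 d | 70 d |
|---|---|---|---|---|---|
| 1% | 0 | 12.2% | 7.7% | 6.8% | 4.9% |
| 2% | 0 | 23.1% | 14.9% | 13.2% | 9.6% |
| 5% | 0 | 48.7% | 33.7% | 30.2% | 22.6% |
| 10% | 0 | 74.6% | 57.0% | 52.2% | 41.0% |
| 5% | 0.3 | 21.8% | 17.9% | 16.9% | 14.4% |
| 5% | 0.6 | 12.3% | 10.9% | 10.5% | 9.6% |

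At p = 5% the 28- versus 50-day gap is 18.5 points with independence, 4.9 at r = 0.3 and 1.8 at r = 0.6. Over p = 1-10% and r = 0, 0.3 and 0.6, the ratio runs from about 1.2 to 1.8.

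**5. What would cancel it.** Expected sets are equal when follow-up in the >38 group is 7.30 / 13.04 = 0.56 of that in the <=30 group (28- versus 50-day cycles), or 7.30 / 9.61 = 0.76 (38- versus 50-day).

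**6. Time since last injection at TPnV1.** This is L - 21: 7 days at L = 28, 17.4 at the 38-week cut and 27.7 at the 30-week cut. It also differs by group.

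**The case against.** **The effect is conditional.** The by-duration tables start at v3.0 consent, not at year 2. Amended-phase time in year 1 follows Protocol Table 1, which samples more densely: about 10 to 22 sets per year for cycles of 49 days or more. Year 1 cycles are nominally at least 49 days, so that time belongs to the <=30 range and raises sampling there. Separately, SAP 2.4.3 counts a single incomplete cycle of 28 days or more as complete. At 30 days this gives 365 / 30 x 4 = 48.7 weeks per year, so someone with very few samples enters the >38 group; this applies up to 38 days. Both points stand and work against the expected direction. The documents do not say how many participants they affect.

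**Only some rows are affected.** By-visit rows have their own denominators and are not inflated. This stands. They are a weak substitute at the extremes, though: under SAP 2.2.4 the next cycle's predose value is also allocated to the preceding cycle, at about day 29 (Week 4) for a 28-day cycle and day 51 (Week 7) for a 50-day cycle.

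**Adverse events cover the serious cases.** Clinically significant abnormalities are recorded as adverse events (Protocol 8.2.6 and 10.4.1), and the overview with rates is repeated by duration group. This limits the consequence. Person-time rates, however, adjust for length of follow-up, not for looks per unit of time.

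**The study is descriptive and groups follow clinical need.** True: even with equal sampling, a gradient could not be attributed to dosing. That limits what the fix can achieve but does not justify leaving a known artefact in the table.

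**Conclusion.** The point holds for the worst-case rows, and the counts drawn from them, in the five by-duration tables. It is an expectation under the year 2 schedule at similar amended-phase follow-up. The direction is the same in every equal-follow-up scenario run. The size rests on assumed p and correlation: strong within-person correlation reduces a large gap to a small one, so no single figure should be quoted as the bias.

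Three stronger readings are tempting but unsupported:
- That the most-treated group will show more abnormalities. The year 1 and single-cycle offsets are unquantified, so this cannot be asserted.
- That an absent gradient is equally untrustworthy. Unequal sampling on the year 2 schedule pushes towards a gradient, and the documents give no direction for any effect of time since injection, so this does not follow from the sampling argument.
- That the by-duration safety tables as a whole, or the primary endpoint, are compromised. By-visit rows and adverse-event tables are not subject to this worst-case rule.

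This is worth correcting because the fix is cheap and the question is one the SAP set out to examine.

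**What to change.** In Tables 14.3.2.2B, 14.3.2.3B, 14.3.3.2B, 14.3.4.2B and 14.3.4.3B:
- Add, by group, the percentage of evaluable post-baseline samples that are abnormal. With no drug effect and a common p, its expectation is p in every group whatever the number of samples. State how unscheduled repeats are counted, since Protocol 8.2.6 calls for repeating clinically significant abnormal tests.
- Show the number of evaluable samples per participant and the amended-phase follow-up time in each group. This also exposes the year 1 and single-cycle offsets.
- Keep the worst-case row, with a footnote that sampling frequency and time since last injection differ by group and that the row should not be compared across groups.

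Two more elaborate remedies are not worth their cost. Splitting by days since injection nearly reproduces the groups (working, step 6) and leaves sparse cells. Keeping one value per 16-week interval retains about 365 / 112 = 3.3 of 13 yearly samples in the group of most safety interest.

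Cost: SAP wording and programming on data already collected, a few extra rows, and a less striking any-abnormality comparison. No visit, sample or protocol amendment is needed.
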